5.4.2. Considerations in Defining Pneumonia

No single definition of pneumonia severity would meet all needs [Brown, 2011]. In addition, there are challenges in accurately distinguishing the types and severity of pneumonia in the GP and hospital record without the confirmation of chest x-ray results, analysis of sputum sample for type of bacterial infection, etc. However, this information may not be collected depending on the healthcare setting and clinical presentation; on the other hand, COPD exacerbations can be associated with the identification of organisms in sputa without presence of pneumonia. The type of pneumonia and underlying organism may be critical to determining appropriate treatment and prognosis [Brown, 2011].

In addition, there are additional difficulties in identifying CAP using primary care, particularly using primary care databases. Several scenarios can occur to further complicate CAP diagnosis in primary care, e.g. (1) CAP will be diagnosed later than the real disease start and recorded only after the medical investigation confirms the working medical diagnosis; (2) CAP will be a consequence or a complication of a previous infectious disease or a COPD exacerbation, or (3) CAP will be later rejected by further clinical evidence. (4) health-care acquired pneumonia, including HAP, could be misdiagnosed as CAP, particularly in patients who seek healthcare frequently. It is not possible to fully address these caveats in a primary care database. But, these were considered when defining the CAP diagnosis and episode. A validation study of CAP requiring hospitalization [Meropol, 2012] and the availability of the CPRD-GOLD linkage to HES improves the ability to identify severe pneumonia (e.g., involving hospitalization).

Each pneumonia will be classified as an episode, with a start date and end date based on the type of pneumonia. In the case of CAP, treatment may precede diagnosis by up to 3

days. Defining the episode will allow distinction between pneumonia episodes that occur in the baseline period (prior to Cohort Entry Date) versus following cohort entry. Recurrent episodes will not be calculated in the study.

5.4.3. Pneumonia Definitions

Several pneumonia outcomes will be defined for this study based on what is recorded in HES and/or the GP record. Distinctions will be made between episodes of severe and non-severe pneumonia events as follows:

- Non-Severe CAP
- Severe pneumonia
 - Severe CAP (CAP requiring hospitalization or resulting in death)
 - Hospital-acquired pneumonia (HAP)

These are defined below. The above categories identify three main classification categories of pneumonia that differ in etiology, severity, and prognosis.

CAP episodes will be identified and classified as severe (requiring hospitalization) or non-severe.

CAP will be based on definitions used previously in CPRD-GOLD [Müllerova, 2012] and those published by others [Meropol, 2012], which have undergone extensive review and evaluation. For this study, a more specific definition will be applied to allow inclusion of only those pneumonia events (versus influenza or other respiratory infection) that occur in the community. As a secondary analysis, the more sensitive definition would be used in sensitivity analysis.

Non-Severe CAP will be classified as an episode of pneumonia that was treated in the community and did not result in hospitalization or death. It would be tabulated based on examining pneumonia episodes and subtracting away any severe CAP or HAP.

Severe CAP will be classified based on hospitalization or death due to pneumonia during the CAP episode. The following CAP would be considered as serious:

- Pneumonia episode that do not involve hospitalization and patient dies during the episode (CPRD-GOLD) OR
- Pneumonia episode that results in hospitalization, where pneumonia was recorded prior to hospitalization (CPRD-GOLD) or within the first 2 days of admission to hospital (HES). If recorded in HES, pneumonia could be recorded on any episode within a spell in any position (e.g., primary or secondary).

The codes denoting pneumonia include all ICD-10 codes for Influenza and pneumonia (J09 to J18) except J09, J10.1, J10.8, J11.1, and J11.8:

In HES, spells represent an admission to the hospital and are comprised of a series of care episodes. Each care episode has a primary diagnosis and secondary diagnosis, where the secondary diagnoses are a series of significant co-morbid conditions. Most hospital

admissions (>90%) have only one episode of care. Based on the nature of the care received, each spell has a healthcare related group (HRG) assigned to it that corresponds to the highest level of care needed.

Hospital-acquired pneumonia or HAP will be classified as a pneumonia episode that was not acquired in the community but was acquired in the hospital (based on HES). Typically, HAP is diagnosed in the hospital >2 days following admission. Pneumonia diagnosed within the first 2 days of hospitalization would be considered severe CAP.

For the purposes of pneumonia outcomes, we will examine all episodes of pneumonia within a spell. Pneumonia diagnoses that occur during any episode within a spell 3 or more days following admission would be considered HAP.

Unfortunately, there was only 1 HAP identified during the subsequent feasibility analysis prior to study conduct based on the date that pneumonia was recorded in the hospital. This raises concern about the ability to distinguish HAP from severe CAP in databases. Initial feasibility indicated the potential to identify HAP; however, a programming error was identified. Given the limited number of HAP, it could not be evaluated separately in the analyses and was combined with severe CAP.

Algorithms would be evaluated to prevent from double counting a single episode as one type of pneumonia. Pneumonia episodes would be classified first as HAP, then severe CAP, and the remaining would be considered CAP based on their relative severity and risk of mortality. It is acknowledged that coding anomalies may exist but be relatively infrequent, for example, there will be pneumonia episodes that may have codes suggested as CAP prior to hospital admission, but an individual patient may be diagnosed with HAP based on their HES information instead of CAP.

5.4.4. Pneumonia Episodes

As pneumonia could be recorded during the baseline period and/or following the Cohort Entry Date and last for a significant period of time, pneumonia will be identified using episodes in a similar manner to COPD exacerbations episodes (start and end dates). We base the assumptions on the definition of pneumonia episodes on prior work [Müllerova, 2012], and prior consultation regarding pneumonia clinical course and resolution patterns.

Although the focus in this study does not involve measuring recurrence as an endpoint, definitions of pneumonia episodes are important to distinguish between those that are in the baseline period (prior to being classified as a new user), on-going at the Cohort Entry Date, or in the cohort follow-up period. In addition, the number of prior pneumonia episodes in the baseline period may be an important factor relating to the risk of pneumonia in the analysis. Patients with on-going pneumonia episodes during cohort entry or with pneumonia that ended with 14 days of the cohort entry date would be excluded from the analysis. During the follow-up period, only the **FIRST** episode of pneumonia per person would be characterized Note: The entire first episode would be examined to distinguish between non-severe CAP, severe CAP, and HAP.

In a prior CAP study conducted by GSK using CPRD-GOLD [Müllerova, 2012], a pneumonia definition was postulated based on a prior consultation with [name]

[name]. The pneumonia episode length was estimated to last approximately 10 weeks (70 days) based on the following assumptions: 77% of COPD patients are expected to be managed at home to recover from CAP back to baseline clinical status within 42 days (6 weeks). Furthermore, it is expected that radiological changes would take longer, with 88% of patients exhibiting return to baseline chest X-ray by ten weeks following the CAP episode start. Therefore, an episode of pneumonia will be considered to last up to 70 days or longer (see below).

The CAP pneumonia episodes are defined as follows:

Start Date for CAP Episodes:

Non-severe CAP and severe CAP in the baseline period will be recorded as indicator variable s (yes/no) and the number of events based on the one-year period prior to Cohort Entry Date. The start of the first CAP episode is the 1st pneumonia event (diagnosis or antibiotics within 3 days prior to diagnosis) in the year prior to Cohort Entry Date. If antibiotics are provided in the 3 days prior to the pneumonia diagnosis, the start date will be the date of antibiotics prescription. The pneumonia end date will be at least 70 days with some exceptions (see below).

For all CAP episodes, we will look back to confirm if an episode is at least 14 days after the end of any prior pneumonia episode. In the follow-up period (after Cohort Entry), patients with CAP or HAP that has not ended at least 14 days prior to the Cohort entry Date will be excluded from the analysis.

End Date for CAP Episodes:

Applying to all CAP episodes, the **end of episode** was defined as 70 days after the start of the episode with some exceptions. The end date can shift under these scenarios: 1) if hospital discharge date for pneumonia CAP is after 70 days, end of the event is set to the discharge date 2) if the patient dies or available data in HES or CPRD-GOLD ends prior to 70 days, end date is set to date of death or data end date, or 3) if there is another pneumonia diagnosis or antibiotic prescribed 14 days following the 70-day end date, the end date is set to the date of antibiotics prescription or 4) if there is hospitalization for pneumonia within the 14-day period after the 70 days, the end date is set to the hospital discharge date,

This check is repeated until a period of 14 days is found, free of a pneumonia event and antibiotics prescription.

CAP episodes would then be classified based on severity (e.g., resulted in hospitalization) during the episode.

The HAP pneumonia episodes are defined as follows:

Start Date for HAP Episodes:

HAP in the baseline period will be recorded as indicator variables (yes/no) and the number of events based on the one-year period prior to Cohort Entry Date. The start of

the first HAP episode is the 1st non-CAP pneumonia event where pneumonia was diagnosed >2 days following admission to hospital. The pneumonia end date will be at least 70 days with some exceptions (see below).

For all HAP episodes, we will look back to confirm if the start of an episode is at least 14 days after the end of any prior pneumonia episode. In the follow-up period (after Cohort Entry), patients with CAP or HAP that has not ended at least 14 days prior to the Cohort entry Date will be excluded from the analysis.

End Date for HAP Episodes:

Applying to all HAP episodes, the **end of episode** was defined as 70 days after the start of the episode with some exceptions. The end date can shift under these scenarios: 1) if hospital discharge date for pneumonia CAP is after 70 days, end of the event is set to the discharge date 2) if the patient dies or available data in HES or CPRD-GOLD ends prior to 70 days, end date is set to date of death or data end, or 3) if there is another pneumonia diagnosis or antibiotic prescribed 14 days following the 70-day end date the end date is set to the end date of antibiotics prescription, or 4) if there is hospitalization for pneumonia within the 14-day period after the 70 days, the end date is set to the hospital discharge date.

This check is repeated until a period of 14 days is found, free of a pneumonia event and antibiotics events.

5.4.5. Created Pneumonia Variables

It is anticipated that the following variables would be created for all pneumonia episodes:

- Non-severe CAP (yes/no)
- Severe Pneumonia
 - Severe CAP (yes/no)
 - HAP (yes/no)
- Start Date of episode
- End Date of episode
- Episode in baseline period (yes/no)
- Episode in the follow-up period (yes/no)
- Note: Patients with an episode has not ended at least 14 days prior to the Cohort Entry Date (yes/no)- would be excluded from analysis

For each patient, the following variables would be created:

- Non-severe CAP at baseline? (Yes/No) During follow-up? (Yes/No)
- Severe CAP at baseline? (Yes/No) During follow-up? (Yes/No)
- HAP at baseline? (Yes/No) During follow-up? (Yes/No)

- Number of Non-severe CAP at baseline
- Number of Severe CAP at baseline
- Number of HAP at baseline
- Time to first pneumonia event or censoring days in follow-up period for each type of pneumonia separately

5.5. Exposure

The primary exposure of interest is ICS, evaluated in new user cohort of ICS-containing medications. The comparator exposure group of interest is LABD.

To account for poor adherence to respiratory medications, patients will be classified as exposed to study medication for the duration of prescribed therapy plus 30 days. When the duration of prescribed therapy cannot be determined due to missing information, it will be assumed to be a 30-day supply to correspond to the amount of medications in a single inhaler. In the case of a single inhaler, patients will allow for gaps of up to 90 days between prescriptions.

To identify a study population of long-term users, we will conduct a secondary analyses restricted to patients on treatment for greater than 6 months. The long-term users would allow for examination of cumulative doses. Gaps between each dispensing of up to 90 days will be allowed. A patient dispensed a single inhaler on the Cohort Entry Date would be censored at 90 days if they did not have another prescription. A patient dispensed a single inhaler on day 40 would experience 99 days of coverage (i.e., 39 days of coverage for the first inhaler and 90 days for the second inhaler).

The strength of the new user prescribed ICS medication on the Cohort Entry Date will be categorized into equipotent doses of low, medium, and high-dose ICS based on classification according to Figure 3-1 presented in the Global Initiative for Asthma (GINA) guidelines [GINA, 2011]. The strength of the new user prescription would be entered into the Cox model primary outcome models as low, medium, and high relative to LABD (e.g. dummy variables). The strength of the medication will be tabulated based on the prescription on the Cohort Entry Date.

The use of other medications during the one-year **Baseline Period** will be included in the model as a marker of disease severity.

Prescriptions (Yes/No) during the Baseline Period indicative of disease severity. In addition, the number of prescriptions (except oxygen use) for the following will be collected:

- short-acting bronchodilators (short-acting anticholinergics or short-acting betaagonists, including combination inhalers)
- long-term oral corticosteroid use (>4 Rx in 12 months)
- theophyllines

- oxygen use. when recorded (changes in reimbursement censor this information during part of the analysis period, but we will capture what information is available)
- nebulized therapy (associated with severity / frailty)
- Daxas (roflumilast) if numbers are sufficient (approved in June 2010 (and may be 0 for most patients)

Exposure "counts" of medications will be categorized during analysis (e.g., tabular summaries, propensity score creation, Cox modeling).

5.6. Confounders

Key risk factors for pneumonia that may also relate to treatment will be measured in the one-year Baseline Period. For the purposes of general co-morbidity assessment and vaccination for pneumonia, a longer history will be examined. Although patients may have varying periods of history, this is not expected to be differentially recorded by treatment (which could result in information bias). A longer look back period is needed to identify co-morbidities given they may not be recorded in the Baseline Period.

Confounders that are based on "counts" of healthcare encounters and exacerbation will be categorized during analysis (e.g., tabular summaries, propensity score creation, Cox modeling).

Variable	Parameterization
Age at Cohort Entry	Age will be treated either as a continuous variable, or as a categorical one (see Table shells for intervals)
Gender	Male=1 or Female=0
Body Mass Index (BMI) during Ever in Patient History	Weight in kilograms divided by height in meters squared, will be utilised as a categorical variable using the following categories widely referenced as WHO classification: Underweight (Below 18.5), Normal (18.5 - 24.9), Overweight (25.0 - 29.9), and Obese (30.0 and greater).
	For modelling, the following cutoff values will also be examined: BMI<21, BMI 21-24.9, BMI ≥25.
Smoking status during Ever in Patient History	Four categories will be created: ex-smoker, current smoker, non-smoker, and unknown smoking status containing patients with missing entries or other types of tobacco exposure (e.g. passive smoking). Non-smoker will be the referent group in modelling.
Overall Social Deprivation Scores for England	The deprivation quintile is derived the 32,482 areas of social deprivation, with 1 being most deprived and 32,482 being least deprived. quintiles will be identified as follows (with least deprived the referent in modelling). Quintiles are provided by CPRD:

Variable	Parameterization
Townsend Scores	Quintile. Townsend scores will be described by quintile, as provided by CPRD-GOLD.
Charlson Co-morbidity index and individual chapters Ever in Patient History (prior to Cohort Entry Date)	Charlson's comorbidity index chapter indicator measures will be created using a recently published algorithm by Khan and colleagues [Khan, 2010] after removing COPD and AIDS from the disease list. Some patients may have COPD and some may not (incident diagnosis). AIDS will be excluded due to very low prevalence in the general population.
	In addition, individual indicator variables will be retained for conditions that contribute to the overall Charlson index, including indicators for the following (1=Yes, 0=No): • AIDS (excluded) • Cerebrovascular disease • Chronic pulmonary disease (excluded) • Congestive heart disease • Dementia • Diabetes • Diabetes • Diabetes • Diabetes with complications • Hemiplegia and paraplegia • Mild liver disease • Moderate or severe liver disease • Myocardial infarction • Peptic ulcer disease • Peripheral vascular disease • Renal disease • Rheumatological disease
Additional Co	 Metastatic tumour 1=Vas_0=No for each condition (over in the nationt's history)
Additional Co- morbidities Ever in patient history (prior to Cohort entry Date): Depression, Anxiety, Asthma, GERD	 I = r es, 0=No for each condition (ever in the patient's history) Anxiety diagnosis or anxiety medications (since diagnosis is underrecorded) Depression diagnosis or anti-depressants (since diagnosed underrecorded) Asthma diagnosis GERD diagnosis or GERD treatments
Co-Medications of Interest associated previously with CAP in Baseline Period	 Statins ACE-inhibitors Immunosuppressive treatment including antiretroviral medications

Variable	Parameterization
COPD severity during Baseline Period (1-Year Prior to and 3 Mo	will be defined according to GOLD-defined lung obstruction based classification with Gold Stage II as the referent in modeling.
Date)	• COPD diagnosis and spirometry mismatch: COPD diagnosis but not according to spirometry
	• GOLD 0: $FEV_1/FVC \ge 70\%$ and $FEV1\%$ predicted $< 80\%$
	• GOLD 1: FEV ₁ /FVC<70% and FEV1% predicted \geq 80%
	• GOLD 2: FEV ₁ /FVC<70% and FEV1 % predicted \geq 50 - <80%
	• GOLD 3: FEV ₁ /FVC<70% and FEV1% predicted \geq 30 - <50%
	• GOLD 4: $FEV_1/FVC < 70\%$ and $FEV_1 \%$ predicted $< 30\%$
	• Unknown (if missing spirometry during the one-year baseline period to 3 months following Cohort Entry Date)
Number of GP visits in One-Year Baseline Period	One encounter will be allowed per day to avoid counting several records referring to a single healthcare visit.
Number of Moderate and Number of Severe COPD Exacerbations in One-Year Baseline Period	 COPD exacerbations are characterized as 'episodes' and consist of two sub-types (1) 'severe' episode characterized with hospitalization for COPD, and (2) 'moderate' episode also called as 'community-treated' characterized with management with COPD-specific antibiotics, oral corticosteroids and/or COPD exacerbation medical diagnosis. Each episode can consist of one or more events, i.e. hospitalization for COPD, management with COPD-specific antibiotics, oral corticosteroids and/or COPD exacerbation medical diagnosis, which occur within a pre-defined time interval. All these events will be flagged in order to allow for tabulation and determination of severity and start/end dates. If a hospitalization for COPD occurs then the exacerbation episode is called 'severe' episode. Episodes will be counted for each person in the baseline period: Each event will have a set of indicator variables Moderate Exacerbation (yes/no) Severe Exacerbation (yes/no)

Variable	Parameterization
	Each person will have a summary measure for the count of exacerbations in the Baseline Period (for subsequent propensity score adjustment rather than the yes/no dichotomous variable).
	Number of moderate exacerbations
	• Number of severe exacerbations Algorithms for exacerbation will be based on prior work within GSK.
Number of Emergency Hospitalizations in One- Year Baseline Period	 Spells whose first episode is an emergency admission on the first episode within a spell. Emergency admissions are based on one of the following categories in HES for ADMIMETH: 21 = Emergency: via Accident and Emergency (A&E) services, including the casualty department of the provider
	• 22 = Emergency: via general practitioner (GP)
	• 23 = Emergency: via Bed Bureau, including the Central Bureau
	• 24 = Emergency: via consultant outpatient clinic
	• 28 = Emergency: other means, including patients who arrive via the A&E department of another healthcare provider
Number of Non- Emergency Hospitalizations in One- Year Baseline Period	Spells whose first episode is a non-emergency admission within a spell. This includes all categories other than those in the emergency section including unknown reasons. Admissions due to delivery of a baby, etc. are included for completeness but not expected with the exception of data anomaly.
	• 11 = Elective: from waiting list
	• 12 = Elective: booked
	• 13 = Elective: planned
	• 31 = Maternity: where the baby was delivered after the mother's admission
	• 32 = Maternity: where the baby was delivered before the mother's admission
	• 81 = Transfer of any admitted patient from another hospital provider other than in an emergency; this does not include admissions to high security psychiatric hospitals (HSPH)
	• 82 = Other: babies born in health care provider
	• 83 = Other: babies born outside the health care

Variable	Parameterization
	 provider, except when born at home as intended 84 = Admission by the admission panel of an HSPH; patient not entered on the HSPH admissions waiting list (not valid for admissions after 31 March 2002) 89 = From the admissions waiting list of an HSPH (not valid for admissions after 31 March 2002) 98 = Not applicable (e.g. other maternity event) 99 = Not known
Number of non-severe CAP Baseline Period (no hospitalization or death)	Number of non-Severe CAP and Dichotomous variable (1=yes, 0=No)
Number of severe CAP in Baseline Period	Number of Severe CAP and dichotomous variable (1=Yes, 0=No)
Number of HAP in Baseline period	Number of HAP and dichotomous variable (1=Yes, 0=No)
Prior vaccination for influenza in Baseline Period	Influenza vaccination in the year prior to cohort entry (1=Yes, 0=No)
Prior vaccination for pneumonia in past 5- years	Pneumococcal vaccination in the 5-year prior to cohort entry based on recommended frequency of vaccination in the UK (1=Yes, 0=No)
Medical Research Council (MRC) dyspnea scale.	 MRC value if recorded in the year prior to 3 months following Cohort Entry Date will be included in modeling. If unknown, "unknown" would be the assigned value. Grade 1: No Dyspnea except on strenuous Exercise Grade 2: Short of breath when walking up a short hill Grade 3: Dyspnea limits walking pace (slower than others) and stops to catch breath Grade 4: Stops to catch breath after walking 100 meters (328 feet) on level ground Grade 5: Dyspnea prevents leaving house and performing Activities of Daily Living Unknown / Unavailable Collapsing of responses into fewer categories will be considered during the analysis
Entry	2007, 2008, 2009, 2010. During modeling, 2002 will be the reference year.

Additional parameterization of the data, including grouping of the count data into categories, will be considered during the creation of PS or modeling based on the distribution of the data. Details of the analysis and modeling strategy will be described in a statistical analysis plan.

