5.7.2. Patient Follow-up Time from Cohort Entry

Patients will be followed from the date of their first eligible prescription (New User entry date) until the earliest of the following:

- date of treatment end (up to 90-day gap allowed for each inhaler),
- date of study end point (first pneumonia event of interest)
- date of transfer to a new practice / practice stops participating or CPRD ends,
- date of ICS initiation (among LABD new users)
- death or
- HES data ends (last available HES data)

As part of the primary analysis, patients will be examined for their first pneumonia (severe CAP, HAP, or non-severe CAP). For example, a patient who has HAP and then

another year has a severe CAP would be considered only for his first event, the HAP. For the analysis of severe CAP, this same patient would be censored on the start date of their HAP episode.

Each patient will have a time and "censoring" variable, which is an indicator variable (yes/no) that indicates 1 if they have had the event of interest or 0 if they are censored. Time will be calculated as the date of the event or censoring minus the cohort entry date plus 1.

Incidence rates of the pneumonia outcomes will be calculated as the number of patients experiencing an event divided by the person-years at risk. Incidence rate ratios were calculated as the incidence rate in the ICS-containing group divided by the incidence rate in the LABD group. Precision of effect estimates will be evaluated from the width of the 95% CIs.

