As a result of the subsequent feasibility prior to the conduct of the study, this protocol was amended to improve precision. The study period was expanded to include more patients and pneumonia events. In addition, the pneumonia endpoints were grouped as severe events (1 HAP and all severe CAP combined). In addition, an overall pneumonia outcome was included rather than severe CAP and non-severe CAP in order to improve on precision and to inform on pneumonia overall. There are also known limitations of database analyses, including the potential for confounding by severity. ICS-containing medications may be dispensed to patients who have more severe COPD or those at higher risk for exacerbation than patients who are receiving long-acting bronchodilators alone. In this study, we will adjust for disease severity in the year prior to initiation using propensity scores, including lung function, exacerbation history, pneumonia history, smoking status, and treatment. Only diagnosed diseases are recorded in CPRD-GOLD. Medication use in CPRD-GOLD is based on prescribed medications recorded by the GP. which might not have been dispensed at the pharmacy or ultimately utilized by the patient. Diagnostic practices for pneumonia may be different in the UK compared with other countries limiting the generalizability. A final disadvantage is that this study does not include the investigational combination inhaled medication FF/VI, but rather can only examine approved ICS-containing medications in this retrospective cohort design.

When identifying pneumonia in databases, definitions are based upon existing information collected in routine healthcare which may not include all details measured in clinical trials. In addition, there is lack of agreement between pneumonia classification in the absence of chest x-rays, sputum, etc. Our definitions were based on using HES for hospitalization and built upon prior work (including validation of severe CAP). There may be some confusion between diagnoses of pneumonia versus influenza-related morbidity.

Despite the limitations, this study will provide insights into risk factors for all pneumonias and severe pneumonia, including whether ICS modify the effect of risk factors for severe pneumonia. The results may identify more specific patient groups that are at greatest risk of severe pneumonia and may identify where risk minimization and/or medical recommendations may be appropriate.

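### Follow-up starts at the first prescription with no lag and the propensity score has no recency term, so pneumonia already developing at that visit can count as an on-treatment event

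*Protocol*

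**What the plan says.** **Start of follow-up.** Protocol Section 5.7.2: "Patients will be followed from the date of their first eligible prescription (New User entry date) until the earliest of the following". The entry date is day 1: "Time will be calculated as the date of the event or censoring minus the cohort entry date plus 1". The event and censoring lists in Sections 5.7.2 and 5.7.4 contain no lag and no exclusion of early events.

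**Acute history in the propensity score.** Section 5.6 gives exacerbations as numbers of moderate and severe episodes over the baseline year: "Each person will have a summary measure for the count of exacerbations in the Baseline Period". It prefers the count to a yes/no variable. Episode dates are nevertheless derived: "All these events will be flagged in order to allow for tabulation and determination of severity and start/end dates". Emergency admissions ("Number of Emergency Hospitalizations in One- Year Baseline Period"), GP visits and prior non-severe CAP, severe CAP and HAP also enter over the baseline year, without recency. Section 5.5 takes oral corticosteroids only as long-term use (more than 4 prescriptions in 12 months).

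**Safeguards at entry.** Section 5.4.4 excludes patients whose recorded pneumonia is on-going at entry or ended within 14 days of it. An episode lasts 70 days by default. CAP onset is moved back to an antibiotic prescribed up to 3 days before the diagnosis.

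**Acknowledged difficulties.** Section 5.4.2 lists these scenarios: "CAP will be diagnosed later than the real disease start and recorded only after the medical investigation confirms the working medical diagnosis" and "CAP will be a consequence or a complication of a previous infectious disease or a COPD exacerbation". Section 6 adds: "ICS-containing medications may be dispensed to patients who have more severe COPD or those at higher risk for exacerbation".

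**The concern.** A new maintenance inhaler may be started at a visit for an acute respiratory episode. Some of those patients may already have a pneumonia that is coded only days later. Such a case is not an effect of the new drug, but the protocol can count it as an on-treatment event.

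The propensity score cannot separate these patients from others. One exacerbation the day before entry and one eleven months earlier give the same value. Section 5.2 looks at history up to and including the new-user date, whereas Section 5.2.1 defines the Baseline Period as the year before entry. So it is also unsettled whether an exacerbation recorded on the prescription date is counted at all.

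At stake is the primary hazard ratio for severe pneumonia, which Section 3 says goes to regulators to inform risk minimization. If acute-visit starts are unequal between arms after weighting, the ratio carries a bias that the listed covariates were not built to remove.

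**Working it through.** **1. What passes the safeguards.** Barring death or end of data, a recorded pneumonia that began within about 70 + 14 = 84 days before entry excludes the patient. That rule needs a recorded pneumonia. Suppose it is not yet recorded and an antibiotic is given on the entry date:
- Coded within 3 days of the antibiotic: onset moves back to the entry date, and the on-going-pneumonia exclusion should apply.
- Coded on day 5 (four days after the antibiotic): not moved back, so it counts as an event.
- No antibiotic in the 3 days before the code: not moved back, so it counts.

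Section 5.4.4 judges severity over the whole first episode, so a counted case becomes a primary event if admission follows.

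**2. Event base.** Section 5.7.8 uses 6,600 LABD and 12,000 ICS users. Treating each patient as one person-year (PY):
- Severe: 6,600 × 0.004 + 12,000 × 0.0074 = 115.2 events; power 0.828 by a two-proportion test (stated: 115 and 82%).
- All pneumonia: 6,600 × 0.011 + 12,000 × 0.0164 = 269.4 events; power 0.852 (stated: 270 and 85%).

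The plan's figures reproduce and are not in dispute. Table 4 gives 106 severe CAP + 1 HAP = 107 severe events, and 283 in all. Table 1 gives an ICS share of a = 12,065/18,742 = 0.644.

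**3. Early events at a flat hazard** (assumption: everyone at risk throughout the window).
- 30 days: 18,742 × 30/365 = 1,540 PY. At the stated 5.3 per 1,000 PY this is 8.2 severe events. The all-pneumonia figures imply 283/0.0158 = 17,911 PY; at 107/17,911 = 5.97 per 1,000 PY it is 9.2.
- 14 days: 18,742 × 14/365 = 719 PY, giving 3.8 to 4.3.

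These counts cover both arms. The ICS share at 30 days is about 5.3 to 5.9.

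**4. Illustrative bias.** The protocol gives no event counts by time since entry, so only a range is possible. Assume no true effect, person-time proportional to patients, no weighting, and the total held at D = 107. Let k be the net excess of already-developing cases in the ICS arm:

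ratio = 1 + k / [a(D − k)]

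| k | Calculation | Crude ratio | Upper 95% limit |
|---|---|---|---|
| 0 | – | 1.00 | 1.49 |
| 5 | 1 + 5/(0.644 × 102) | 1.08 | 1.61 |
| 10 | 1 + 10/(0.644 × 97) | 1.16 | 1.74 |
| 15 | 1 + 15/(0.644 × 92) | 1.25 | 1.89 |

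Upper limit = ratio × exp(1.96 × √(1/ICS events + 1/LABD events)), where ICS events = a(D − k) + k and LABD events = (1 − a)(D − k).

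**5. Plausibility of k.** Against 5.3 to 5.9 expected ICS events in 30 days, k = 10 means about (5.9 + 10)/5.9 = 2.7 to (5.3 + 10)/5.3 = 2.9 times the flat-hazard count. For k = 15 it is about 3.5 to 3.8 times. The larger values need a marked early cluster.

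**The case against.** - **This belongs in the analysis plan.** Sections 5.6, 5.7.4 and 5.7.9 leave further parameterization to it. That stands for details such as grouping counts. But the protocol itself fixes the start of follow-up and chooses the baseline-year count, and a general allowance for refinement supplies neither a recency term nor a lag.
- **Acute history is not reduced to exacerbations.** Correct: emergency admissions, GP visits and prior pneumonia also enter. None carries recency, so the gap remains.
- **The protocol says these caveats cannot be fully addressed.** True of primary care data, but a partial remedy is available from dates already derived.
- **Early events are dropped elsewhere.** The persistent-user analysis in Section 5.7.5 restarts at 6 months with a new propensity score. It is secondary, conditions on persistence, and discards far more than the window in question. The proportionality tests and time-to-event figures could reveal an early cluster but would not correct for it.
- **LABD starters face the same problem.** This stands and is the main limit. A reader might infer that the ICS hazard ratio is certainly inflated. The protocol does not show that: the statement in Section 6 concerns severity and exacerbation risk, not how often treatment starts at an acute visit.
- **The effect is modest.** With 107 events the standard error of the log hazard ratio is 1/√(107 × 0.644 × 0.356) = 0.20, so even a ratio of 1.25 (log 0.22) is a shift of about one standard error. This stands.

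**Conclusion.** The point holds as a gap in the design. Pneumonia developing at the prescribing visit can be counted as an on-treatment event in either arm, and no covariate marks recent acute illness. Upward bias in the severe-pneumonia hazard ratio follows only if acute-visit starts are more common with ICS after weighting; that is plausible but not quantified.

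The size is unknown. Under the stated assumptions, 5 to 15 net excess ICS events move a null crude ratio to about 1.08 to 1.25. From a true null, none of these cases takes the crude upper limit past the margin of 2.0 in Section 5.7.8, though 15 events bring it to about 1.89. Weighting would widen the interval further.

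Two stronger readings go beyond the protocol. A reader might infer that the first weeks carry the highest hazard, but no event timing is given. A reader might also infer that every such case is charged to ICS, but the 84-day reach of the exclusion, the 3-day back-dating and the shared exposure of LABD starters rule that out.

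**What to change.** 1. In Section 5.6, add to the propensity score an indicator (none / moderate / severe) for an exacerbation episode on-going at the Cohort Entry Date, or ended within the 30 days before and including it. The start and end dates are already derived. Including the entry date in the definition also settles, for this covariate, the ambiguity between Sections 5.2 and 5.2.1.
2. In Section 5.7.5, add one sensitivity analysis of the primary outcome that starts at-risk time after 30 days in both arms, among patients still event-free and uncensored.

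**Cost.** One derived covariate and one repeat of the primary model. At a flat hazard the lagged run loses about 8 to 9 severe events. Schoenfeld power for a hazard ratio of 1.85 falls from about 0.86 to 0.83, and the upper limit at a ratio of 1 moves from about 1.49 to 1.51. The lagged run would also omit any true early effect, and the 30-day window is a judgement. It should therefore remain a sensitivity analysis; the main analysis keeps all events.
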